### STUDY SYNOPSIS

Title:	PURE-HF: P eripheral U ltrafiltration for the RE lief from Congestion in H eart F ailure			
Study code:	UF-HF-02-INT			
Study design:	Multicenter, prospective, randomized, parallel-group controlled clinical trial			
Investigational device:	Chiara, peripheral ultrafiltration			
Control device:	not applicable			
Control therapy:	Usual care including high-dose intravenous (IV) diuretics			
Study objectives:	Primary objective			
	To evaluate whether tailored, peripheral ultrafiltration complementary to low-dose diuretics is associated with a reduction in cardiovascular mortality in 90 days after randomization and heart failure events in 90 days after discharge compared to usual care including stepped intravenous diuretics, in acutely decompensated chronic heart failure with fluid overload (not fully responsive to diuretic therapy).			
	Secondary objective			
	The secondary aims will be to examine the effect of the above treatment assignments on:			
	
 
Heart failure rehospitalization analyzed as a recurrent event in 90 days after discharge
 
			
	2. Time until first HF rehospitalization in 90 days after discharge			
	3. Time until first urgent HF visit in 90 days after discharge			
	
 
Quality of life (Patient Global Assessment at baseline, discharge, FU30, FU90; Short Kansas City Cardiomyopathy Questionnaire and EQ-5D-5L at discharge, FU30, FU90)
 
			
	5. Days alive and out of hospital up to 90 days after discharge			
	6. Cardiovascular mortality in 90 days after randomization			
	
 
Resolution of congestion defined as resolution of at least two of the final eligibility criteria present at randomization (this does not include chest x-ray criterion, i.e. if x-ray criterion was one out of two final eligibility criteria, only resolution of the other criterion is necessary), thus:
 
			
	• Jugular venous pressure of $< 8$ cm H 2 O			
	No orthopnea			
	Trace or no peripheral edema			
	
 
Respiratory rate no longer ≥20/minute
 
			
	8. In-hospital worsening heart failure until discharge			
	9. Weight loss at 96h after randomization and at discharge			

**Study hypotheses:** In acutely decompensated chronic heart failure patients who are admitted to the hospital due to symptoms and signs of congestion and who are not fully responsive to diuretic therapy, tailored, peripheral ultrafiltration complementary to low-dose diuretics provides better 90 day outcomes than usual care (guideline-directed medical therapy including IV diuretics).

Version: 5.0

- Patients:Acutely decompensated chronic heart failure patients who are
admitted to the hospital due to symptoms and signs of
congestion and who are not fully responsive to diuretic therapy
- Sample size: Sample size including 10% loss to follow-up and 13% treatment failure is 864 (432 in each group), minimum age of 18 years, no maximum age, both sexes, regions (western, central and eastern Europe).

### Inclusion criteria:

General:

- Informed consent signed and dated by study patient and investigator/authorized physician
- Minimum age of 18 years
- Ability to understand the nature and requirements of the study

### Study-specific:

- Heart failure (HF) patients with preserved, mid-range or reduced ejection fraction (confirmed according to the current definitions of heart failure with preserved (HFpEF), mid-range (HFmrEF) and reduced ejection fraction (HFrEF) requiring echocardiographic assessment within the prior 12 months) who are admitted to the hospital due to signs/symptoms of congestion (left- or right sided)
- On regularly scheduled oral loop diuretics prior to admission
- Patients who have received IV loop diuretics for decongestion within 24 hours after hospital admission and prior to screening. The dosages are administered according to clinical judgment.
- Symptoms of congestion and clinical evidence at the time of screening for eligibility:
  - Fluid overload manifested by at least 2 of the following:
    - Pitting edema  $\geq$ 2+ of the lower extremities
    - Jugular venous pressure >8 cm H2O
    - Pulmonary congestion or pleural effusion on chest x-ray
    - Paroxysmal nocturnal dyspnea or  $\geq 2-$  pillow orthopnea
    - Respiration rate  $\geq$ 20 per minute

• Additional objective documentation of congestion: Lung or inferior vena cava ultrasound, chest x-ray or elevated filling pressures, if available, at the time of randomization (optional)

### Exclusion criteria:

Candidates will be excluded from the study if **ANY** of the following conditions apply:

General:

- Any condition which could interfere with the patient's ability to comply with the study
- In case of female patients: pregnancy or lactation period
- Participation in an interventional clinical study during the preceding 30 days
- Previous participation in the same study
- Unwillingness or inability to complete follow up
- Active drug or alcohol abuse (smoking allowed)

### Study-specific:

- Acute coronary syndrome requiring intervention during index hospitalization
- Severe renal dysfunction requiring renal replacement therapy
- Systolic blood pressure <90 mmHg at the time of randomization
- Pulmonary hypertension not secondary to left heart disease
- Pulmonary disease thought to be primarily responsible for symptoms
- Contraindication to systemic anticoagulation
- Severe concomitant disease expected to prolong hospitalization or to cause death in ≤90 days
- Sepsis
- Severe uncorrected valvular stenosis at the time of randomization
- Active myocarditis
- Hypertrophic obstructive cardiomyopathy
- Constrictive pericarditis or restrictive cardiomyopathy
- Liver cirrhosis due to primary liver disease
- Known infection with human immunodeficiency virus (HIV) or active hepatitis C
- Previous solid organ transplant
- Presence or requirement for mechanical respiratory support
- Presence or requirement of a mechanical circulatory support device
- Need for IV positive inotropic agents at the time of randomization

### Treatment:

### Ultrafiltration group:

Patients in the intervention group will be treated with veno-venous ultrafiltration (UF) complementary to low-dose diuretic therapy according to the low-dose IV diuretic treatment algorithm and other medical therapy as judged indicated by the investigator. Patients will receive 1-7 UF sessions (6-10h/session, number of sessions depending on clinical assessment according to algorithm) during a maximum time period of 10 days.

### Control group:

Patients in the control group will be treated with high-dose diuretic therapy according to the high-dose diuretic treatment algorithm and other medical therapy as judged indicated by the investigator.

### Target variables:

Primary endpoint:

Composite endpoint of cardiovascular mortality in 90 days after randomization and heart failure events in 90 days after discharge. HF events are defined as HF rehospitalization or an urgent HF visit.

Secondary endpoints:

- 1. Heart failure rehospitalization analyzed as a recurrent event in 90 days after discharge
- 2. Time until first HF rehospitalization in 90 days after discharge
- 3. Time until first urgent HF visit in 90 days after discharge
- Quality of life (Patient Global Assessment at baseline, discharge, FU30, FU90; Short Kansas City Cardiomyopathy Questionnaire and EQ-5D-5L at discharge, FU30, FU90)
- 5. Days alive and out of hospital up to 90 days after discharge
- 6. Cardiovascular mortality in 90 days after randomization
- 7. Resolution of congestion defined as at least two of the final eligibility criteria present at randomization have resolved (this does not include chest x-ray criterion, i.e. if x-ray criterion was one out of two final eligibility criteria, only resolution of the other criterion necessary), thus:
  - Jugular venous pressure of <8cm H2O
  - No orthopnea
  - Trace or no peripheral edema
  - Respiratory rate no longer  $\geq$  20/minute
- 8. In-hospital worsening heart failure until discharge
- 9. Weight loss at 96h after randomization and at discharge

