### **1.2. SECONDARY ANALYSES**

The analysis of secondary endpoints and exploratory variables (see section **Fehler! Verweisquelle konnte nicht gefunden werden.**) including the total number of recurrent HF hospitalizations, weight loss during index hospitalization, duration of index hospitalization (in days), changes in laboratory measurements (e.g. resolution of congestion) as well as "Quality of Life" (short form of KCCQ with EQ-5D as standardized measure of health status) and Patient Global Assessment (PGA) will included in formal analyses. There will be no structured analysis taking into account multiple testing. Summary statistics such as mean, standard deviation [SD], median, 25th [Q1] and 75th [Q3] percentiles, minimum [Min] and maximum [Max]) will be calculated for continuous variables. Frequencies and percentages will be presented for categorical variables.

The comparison between treatment groups will be evaluated using logistic regression analysis adjusting for stratification variables (other than study site) or Fisher's exact test (in case of a rare outcome) for categorical variables, using joint modeling of death and recurrent events in the case of heart failure hospital admissions and linear regression analysis for continuous variables adjusting for stratification variables (other than study site) and, where appropriate for baseline levels of the variable. Non-parametic methods will be used where appropriate.

As described in section 1.1, patients who die or lost to follow-up after discharge are included in all secondary analyses with all available data up to the date of last contact.

Descriptive summaries of KM curves will be presented for all-cause mortality. Patients alive at the end of the study will be censored at the last date known to be alive.

More detailed descriptions of statistical methods and assumptions including calculated variables and the proposed format and content of tables and figures in the final report will be detailed in the Statistical Analysis Plan (SAP). Wherever reasonable, evaluation will be stratified by subgroups (i.e. age, other baseline characteristics) and pre-defined in the SAP. All statistical analyses will be performed using the software package SAS® [SAS Institute Inc., The SAS system for Windows, Cary, NC: SAS Institute Inc., 2013].

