### **1.6.** SAMPLE SIZE JUSTIFICATION

Previously published results from clinical trials comparing intravenous loop diuretics to mechanical fluid removal by isolated veno-venous ultrafiltration have yielded conflicting results regarding heart failure-related rehospitalization. The present PURE-HF study is similar to the AVOID-HF (Costanzo et al., 2015) in terms of study design and targets. The primary objective of the AVOID-HF study was to determine whether UF prolonged the time to first HF event within 90 days of hospital discharge. Regarding sample size considerations, the AVOID-HF trial refers to different publications in order to provide an estimate of the combined HF event rate for the control group and the assumed reduction of the HF event rate in the UF group (Felker et al., 2011, O'Connor et al., 2011, Costanzo et al., 2007, Konstam et al., 2007, Hernandez et al., 2010, Ross et al., 2010).

Taking into account the assumptions and observations actually made in the prematurely terminated AVOID-HF study published by Costanzo et al. (Costanzo et al., 2016) we estimated that 864 patients (432 in each arm) should be sufficient to test whether there is a difference between the event proportions of the test and the control treatment. The proposed sample size calculations based on the two-sided Z test with unpooled variance and include the following assumptions: 1)  $\alpha$  of 0.05 ( $\alpha$ /2=0.025); 2) power (1- $\beta$ ) of 0.90; 3) an HF event rate for the loop diuretics group of 25% plus 2% cardiovascular death and 4) a reduction of the event proportion for the UF group of 37,5 % (this leads to an event proportion for the UF group of 16,88%). The estimated total sample size is displayed with additional patients included to account for 10% of subjects lost to follow-up and 13% treatment failures due to crossover during the treatment period

Event proportion			Sample size N		
control group	UF group	Reduction	Crude	Incl. 10% loss to FU	Incl. 10% loss to FU and 13% treatment failure
27.00%	16.88%	37.50%	694	764	864

- 1) Test for two proportions,
- 2) two-sided a of 0.05,
- 3) power of 0.90,
- 4) HF event rate of control group of 25% + 2% in-hospital death
- 5) an event proportion for the loop diuretics group (control group) of 27%,
- 6) an event proportion for the UF group (treatment group) of 16.88% (37.50% reduction),
- 7) including 10% loss to follow up and 13% crossover (i.e. treatment failure),

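### The short KCCQ and EQ-5D-5L have no pre-treatment measurement, so these two quality-of-life comparisons go without a baseline covariate, at some cost in precision

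*Combined protocol and SAP*

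**What the plan says.** The synopsis lists secondary endpoint 4 twice, under the study objectives and under Target variables, with the same timing in both places. One instrument has a baseline: "Patient Global Assessment at baseline, discharge, FU30, FU90". The other two do not: "Short Kansas City Cardiomyopathy Questionnaire and EQ-5D-5L at discharge, FU30, FU90".

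The randomized treatment is given during the index admission. In the ultrafiltration group, "Patients will receive 1-7 UF sessions" within a period of at most 10 days (synopsis, Treatment). The control algorithm also runs in hospital.

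Section 1.2 includes the short KCCQ, EQ-5D and PGA in the formal analyses. The model for continuous outcomes is "linear regression analysis for continuous variables adjusting for stratification variables (other than study site) and, where appropriate for baseline levels of the variable". Nothing in the text under review supplies a pre-treatment KCCQ or EQ-5D-5L score, or names another covariate to stand in for it.

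**The concern.** The general model in Section 1.2 foresees the baseline level of the outcome as a covariate. For the KCCQ and EQ-5D-5L the earliest score is the one at discharge. That score follows the assigned treatment and is itself listed as an endpoint time, so it cannot serve as a baseline.

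Two things are at stake. First, a baseline score that correlates with follow-up would narrow the confidence intervals at discharge, 30 and 90 days. Second, change from before treatment cannot be reported on either instrument. Since PGA is patient-reported and already scheduled at baseline, a contact exists at which the other two could have been collected.

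**Working it through.** **The plan's own figure.** The only sample size in the plan is for the primary endpoint (Section 1.6). With 27% against 16.88%, two-sided alpha 0.05, power 0.90 and unpooled variance:

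n per arm = (1.960 + 1.2816)² × [0.27 × 0.73 + 0.1688 × 0.8312] / (0.27 − 0.1688)² = 346.2, so 347 per arm and 694 in total, as stated.

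694 × 1.10 = 763.4 (stated 764), and 764 × 1.13 = 863.3 (stated 864). The figure reproduces and does not depend on any quality-of-life input. The documents give no standard deviation (SD), target difference or power for the KCCQ or EQ-5D-5L.

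**Inputs for the quality-of-life check.**
- 432 patients per arm (synopsis, Sample size). After 10% loss to follow-up: 432 × 0.90 = 389.
- r, the correlation between a pre-treatment score and the follow-up score on the same instrument, is not in the documents. It is assumed to lie between 0.2 and 0.6, and is best read as the correlation left after adjusting for the stratification variables, which the model already contains.

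**Formulas.** Adjusting for a baseline present in every patient multiplies the residual variance by 1 − r² and the standard error (SE) by √(1 − r²). The equivalent gain in sample size is 1/(1 − r²) − 1. The last two columns take 389 per arm. The detectable effect is at 80% power: (1.960 + 0.8416) × √(2/389) = 0.201 SD without the baseline, multiplied by √(1 − r²) with it. The power column uses an illustrative effect of 0.2 SD, for which power without the baseline is 79.7%.

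| Assumed r | 1 − r² | SE ratio | Fall in SE | Equivalent extra patients | Detectable effect (SD) | Power at 0.2 SD |
|---|---|---|---|---|---|---|
| 0.2 | 0.96 | 0.980 | 2% | 4% | 0.197 | 81.2% |
| 0.3 | 0.91 | 0.954 | 5% | 10% | 0.192 | 83.2% |
| 0.4 | 0.84 | 0.917 | 8% | 19% | 0.184 | 86.1% |
| 0.5 | 0.75 | 0.866 | 13% | 33% | 0.174 | 89.6% |
| 0.6 | 0.64 | 0.800 | 20% | 56% | 0.161 | 93.7% |

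**Partial capture.** If half the patients have a baseline, the variance falls by about r²/2. At r = 0.5 that is 0.125, so the SE ratio is √0.875 = 0.935. The fall is about 6%, equivalent to 1/0.875 − 1 = 14% more patients.

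**Baseline PGA as substitute.** The same formula applies, but r becomes the correlation of baseline PGA with follow-up KCCQ or EQ-5D-5L. That is a different quantity and is also not given, so the table does not size this gain.

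**The case against.** A reader might infer that the plan contradicts itself because it promises an adjustment that it cannot carry out. The text does not go that far. Section 1.2 adjusts only "where appropriate for baseline levels of the variable"; with no baseline collected, the clause simply does not apply to these two instruments.

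A reader might also fear that the discharge score will be used as the baseline, which would adjust away any effect already present at discharge. No passage proposes this, and the endpoint definition lists discharge as an outcome time. It is a possibility to close off, not a fault in the plan.

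Nor do the documents show that imputation is weakened in any particular way. Section 1.4 leaves the details to the SAP. The discharge score can legitimately help to impute the 30- and 90-day scores and is closer to them in time, and baseline PGA is available too.

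The size can be challenged as well. A baseline taken during acute decompensation may correlate weakly with a score 30 or 90 days after discharge. Full capture is also unlikely: the protocol is at version 5.0 with database lock planned for Q3 2021, and the number of patients still to enrol is not stated. These points stand, and they limit the claim to the range given.

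Finally, the reviewed text contains no schedule of assessments, and the trial-flow figure is not shown. If a schedule elsewhere includes baseline KCCQ and EQ-5D-5L, the synopsis needs to be reconciled with it.

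What survives is the gap itself: two instruments without a pre-treatment value and no named substitute, while PGA has one.

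**Conclusion.** The point holds as a modest, avoidable loss of precision, together with the loss of change-from-pre-treatment reporting, on two of three instruments in one of nine secondary endpoints. It is not a bias: the randomized comparison of KCCQ and EQ-5D-5L is valid without a baseline. PGA, the primary endpoint and the sample size are not touched.

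The direction is certain for any non-zero correlation. The size rests on an assumed r and on a baseline in every patient. It is close to negligible near r = 0.2 and worthwhile from about r = 0.5. This is an improvement worth making because part of it costs nothing, not a defect that endangers the trial.

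**What to change.** (a) Free, and open whatever the state of enrolment. State in the SAP that the KCCQ and EQ-5D-5L models at discharge, 30 and 90 days adjust for baseline PGA as well as the stratification variables, and that the discharge score is an outcome and will not be used as a baseline. This needs no new data, only a sentence or two settled before unblinded analysis. It assumes that baseline PGA is recorded before the assigned treatment starts, as its name implies. The gain may be only part of what a same-instrument baseline would give.

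(b) Cheap, optional, and only for patients still to be enrolled. Give the short KCCQ and EQ-5D-5L at the same baseline contact as PGA, before treatment starts, and analyse by ANCOVA on the baseline score. The SAP should say how patients without a baseline score stay in the model, for example through a missing-baseline indicator. The cost is a protocol change, a few minutes' burden in acutely ill patients, and some missing baselines. If few patients remain to be enrolled, (a) alone is enough.

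### Endpoint 7 reduces up to four congestion signs to one yes/no result with no adjustment for how many were present at entry; an entry-adjusted supportive count would usually recover some power cheaply

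*Combined protocol and SAP*

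**What the plan says.** The synopsis (Target variables, secondary endpoint 7) opens the definition with "Resolution of congestion defined as" and counts congestion as resolved when at least two "of the final eligibility criteria present at randomization have resolved". The chest x-ray is left out of the count, with one exception: "if x-ray criterion was one out of two final eligibility criteria, only resolution of the other criterion necessary". Four signs can count: jugular venous pressure, orthopnea, peripheral edema and respiratory rate.

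The study-specific inclusion criteria require "Fluid overload manifested by at least 2 of the following", from a list of five that includes the x-ray. The number of countable signs at entry can therefore be anything from one (x-ray plus one other) to four.

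Section 1.2 compares categorical variables by "logistic regression analysis adjusting for stratification variables (other than study site"), or by Fisher's exact test if the outcome is rare. Adjustment for a baseline level is mentioned only for continuous variables. The same section lists this endpoint under "changes in laboratory measurements (e.g. resolution of congestion"), allows non-parametric methods where suitable, and leaves fuller detail to the SAP. On multiplicity it says: "There will be no structured analysis taking into account multiple testing". The text supplied contains no ordinal or count analysis of the signs.

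**The concern.** Each patient contributes up to four separately judged signs, but the comparison uses only whether a threshold was crossed. Two things are lost.

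- **Partial and further clearing.** One of two non-x-ray signs cleared is scored like none, and four of four is scored like two of four.
- **Entry severity.** The chance of meeting the target depends strongly on how many signs the patient brought in, yet that number is not in the stated model.

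Relief of congestion is what ultrafiltration is meant to achieve, so a real but moderate difference in bedside signs would be useful in interpreting the primary result. The yes/no form makes it more likely to be missed in data the trial already records.

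**Working it through.** **Inputs from the plan.** Section 1.6 gives 432 per arm and two-sided 5%. Those figures belong to the primary endpoint and they reproduce. With the unpooled Z formula, n per arm = (1.960 + 1.282)² × [0.27×0.73 + 0.1688×0.8312] / (0.27 − 0.1688)² ≈ 346.2, so 347 per arm and 694 in total. Then 694 × 1.10 = 763.4, rounded up to 764, and 764 × 1.13 = 863.3, rounded up to 864. No resolution rate, entry-sign mix, correlation, effect or power is given for endpoint 7.

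**Step 1: what the rule merges.** With k non-x-ray signs at entry, a yes needs min(k, 2) cleared.

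| k | Needed | Results scored alike |
|---|---|---|
| 1 (with x-ray) | 1 | none; yes/no and count are the same variable |
| 2 | 2 | 0 and 1 cleared |
| 3 | 2 | 0 and 1; 2 and 3 |
| 4 | 2 | 0 and 1; 2, 3 and 4 |

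**Step 2: the target's difficulty depends on k.** Suppose each sign clears with probability p = 0.60, independently. The yes rate is:
- k = 1: p = 60%
- k = 2: p² = 36%
- k = 3: p³ + 3p²(1−p) = 0.216 + 0.432 = 65%
- k = 4: 1 − (1−p)⁴ − 4p(1−p)³ = 1 − 0.0256 − 0.1536 = 82%

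With latent correlation 0.5 between signs the last three become about 44%, 62% and 71%. The number of entry signs is therefore strongly prognostic for the yes/no result.

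**Step 3: power.** Simulation with 432 per arm and two-sided 5%; signs are linked by a shared latent normal variable. Both outcomes are adjusted for k where k varies, so the difference isolates the cut. Assumed here: a 0.2 SD shift on every sign and correlation 0.5. Mixes give the percentage of patients with k = 1/2/3/4. Gains were taken before rounding.

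| Entry mix | Control per-sign clearing | Yes rate, control vs UF | Power, yes/no | Power, count | Gain |
|---|---|---|---|---|---|
| all k = 2 | 60% | 44 vs 53% | 74% | 81% | 7 |
| all k = 2 | 75% | 62 vs 70% | 71% | 75% | 4 |
| all k = 3 | 60% | 62 vs 70% | 74% | 87% | 13 |
| all k = 3 | 75% | 79 vs 85% | 66% | 84% | 17 |
| broad, 10/30/35/25 | 60% | 59 vs 67% | 72% | 83% | 11 |
| broad, 10/30/35/25 | 75% | 75 vs 81% | 61% | 79% | 18 |
| x-ray-heavy, 40/40/20/0 | 60% | 54 vs 62% | 68% | 76% | 7 |
| x-ray-heavy, 40/40/20/0 | 75% | 71 vs 77% | 63% | 70% | 7 |

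Hand check of the first row: (0.53 − 0.44) / √[(0.44×0.56 + 0.53×0.47)/432] = 0.09/0.0339 = 2.66, so power ≈ Φ(2.66 − 1.96) = Φ(0.70) ≈ 76%, against 74% simulated.

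Central case (broad mix, 65% per sign, correlation 0.5): 71% for the yes/no result, 82% for the count by linear regression and 83% by proportional odds. With no effect, both outcomes rejected in 4.6 to 5.1% of runs.

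**Step 4: how far the gain moves.** Per-sign clearing was varied from 40 to 85% and correlation from 0.2 to 0.8, with the effect set to give about 80% yes/no power. Monte Carlo error is a few points.
- x-ray plus one sign only: exactly 0
- x-ray-heavy mix: 0 to 10
- all k = 2: 2 to 16
- broad mix: 4 to 17
- all k = 3: 6 to 23
- all k = 4: 6 to 32. The 32 is one corner, where 97% vs 99% resolve; otherwise the maximum is 23.

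Shifts of 0.1 or 0.3 SD at correlation 0.5 gave 1 to 8 points. At a fixed 0.2 SD shift the most extreme inputs gave about 60, which I do not rely on. A 0.3 SD effect on only two of the four signs gave 8 to 13.

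**Step 5: adjustment matters.** Without adjustment for k, the count ranged from 5 points worse than the yes/no result to 7 better in the x-ray-heavy mix, and from 0 to 19 better in the broad mix. Adding k to the yes/no model alone gained about 0 to 6 points.

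**The case against.** The strongest reply is that endpoint 7 asks a different question. It asks whether congestion has cleared to a stated clinical threshold. A count weights four unlike signs equally and credits partial clearing. Making it the main test would change the estimand, not correct an error. That stands, and it is why the yes/no comparison should stay.

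Three further replies have weight:
- Section 1.2 never assigns logistic regression to this endpoint by name. It allows non-parametric methods and defers detail. The link is an inference, and the lack of an ordinal analysis in summary-level text is weak evidence that none is intended.
- Endpoint 9, weight loss, is already a continuous measure of decongestion, so endpoint 7 is not the only evidence on mechanism.
- Signs that share one cause may be highly correlated, and the gain shrinks there. In the x-ray-heavy mix at correlation 0.8 it is about 0 to 3 points.

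A technical reply is that a patient entering with two signs cannot have three or four remaining, so one common odds ratio fits the count imperfectly. The central case shows no power penalty for proportional odds, and linear regression is available, but the odds ratio needs cautious reading.

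A reader might infer a definite loss, with a floor of several points and a ceiling near 30. The documents do not support either bound: the loss is nil for patients entering on x-ray plus one sign, and every other figure depends on inputs that the plan does not give.

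**Conclusion.** The point holds as a cheap improvement. The rule discards recorded information, and the stated model omits a strong prognostic factor. Against an entry-adjusted count, the usual cost is about 5 to 20 points of power. The range is from 0 (x-ray-plus-one-sign patients, x-ray-heavy mixes, highly correlated signs) to about 30 in corner cases. These figures rest on assumed clearing rates, correlations and entry mixes, and on an effect of about 0.2 SD, mostly taken as equal on all signs. They show the direction and likely order of the loss; they are not an estimate for this trial.

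It would be wrong to conclude that the yes/no endpoint is invalid or should become a mere description, because it answers a legitimate question. Nor does the point reach the primary analysis or the 864 patients. It concerns one of nine secondary endpoints that carry no multiplicity control.

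**What to change.** In the SAP:

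1. Keep the pre-specified yes/no comparison and name its model explicitly. Add the number of non-x-ray signs present at randomization as a covariate in that logistic regression. Remove the label that places this endpoint among laboratory changes.
2. Pre-specify a supportive between-arm analysis of the number of non-x-ray entry signs still present (0 to 4), taken at the same assessment as the yes/no result. Use proportional-odds or linear regression, chosen in advance, adjusted for the stratification variables and the number of signs at randomization. Report the common odds ratio or mean difference with its 95% CI.

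The cost is some SAP wording, one covariate and one extra model, with no new visits or data. The downsides are one more secondary analysis without multiplicity control, equal weighting of unlike signs, and an effect measure that is harder to read than a responder percentage.
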